#### 4.2.4 Incomplete dates for the last administration of LCM

For purposes of imputing missing components of partially reported dates for the last administration of LCM, the algorithms listed below will be followed. Stop dates of LCM will be displayed as reported in the subject data listings (ie, no imputed values will be displayed in data listing).

- Missing last administration day, but month and year present:

The last administration day will be set to the last day of the month or the date of the final contact, whichever is earlier in the month.

- Missing last administration day and month, but year present:

The last administration day will be set to the last day of the year or the date of the final contact, whichever is earlier in the year.

- Completely missing date of last administration:

For calculating the duration of exposure, if the date of last administration is completely missing and no information could be obtained from data cleaning exercises, the date of last administration should be imputed as the date of last contact according to the Study Termination eCRF module. For all other purposes, no imputation will be done if the date of last administration is completely missing.

However, if a subject died during the study, and the imputed last administration date according to the rules above is after the date of death, the last administration date will be assigned to the date of death.

#### **4.2.5 Incomplete dates for seizure diary data**

Seizure frequency and seizure-free days will be calculated over non-missing diary days during each time interval; days for which seizure diary data were not obtained will not be considered in the calculation of seizure frequency or seizure-free days. As the evaluation of efficacy is not the primary objective of this study, and because this is an uncontrolled study in a variable setting, which allows individualized optimization of dosing of LCM and concomitant antiepileptic drugs (AEDs), no summaries assessing the impact of missing seizure diary days are planned.

#### **4.2.6 General imputation rule for incomplete dates**

Where necessary for the calculation of derived variables, partial dates will be completed using the earliest calendar date based on the partial date provided. This rule is valid for all partial dates with the exception of the following:

- Start and stop dates of AEs
- Start and stop dates of concomitant medication
- Start and stop dates of LCM
- Start and stop dates of seizure diary data

Completely missing dates will not be replaced and the corresponding derived variables will be set to missing.

### **4.3 Interim analyses and data monitoring**

No formal interim analysis is planned. However, data may be reported prior to the completion of this study to support annual reports, regulatory submissions, and publications.

### **4.4 Multicenter studies**

No multicenter analyses are planned; therefore, this section is not applicable for this study.

#### **4.5 Multiple comparisons/multiplicity**

No statistical testing is planned; therefore, this section is not applicable for this study.

#### **4.6 Use of an efficacy subset of subjects**

The FAS, defined in [Section 3.5.2](#), is the primary analysis set for efficacy analyses. No additional efficacy subsets are defined for this study.

#### **4.7 Active-control studies intended to show equivalence**

This section is not applicable for this study.

#### **4.8 Examination of subgroups**

Subgroups for this study are defined in the sub-sections of [Section 3.2](#).

### **5 STUDY POPULATION CHARACTERISTICS**

#### **5.1 Subject disposition**

An overall summary of disposition will be provided for all screened subjects. All screened subjects is defined as all subjects enrolled into EP0034.

A summary of disposition of subjects will be provided for all screened subjects. The date of first subject in (date of earliest Visit 1 for this study), date of last subject out (date of final scheduled or unscheduled visit), number of screened subjects, and the number of subjects in each analysis set (SS and FAS), will be summarized overall and by investigator site. Subjects who transferred sites will be summarized according to their original site.

A summary of disposition of analysis sets will be provided for all subjects. The following will be summarized:

- The number and percentage of subjects in the SS
- The number and percentage of subjects in the FAS

Additionally, a summary of disposition and discontinuation reasons will present the following for all subjects in the SS (overall and repeated by weight band and enrollment group using the levels defined in [Sections 3.2.10](#) and [3.2.12](#) respectively) and FAS:

- The number and percentage of subjects starting the study
- The number and percentage of subjects completing the study
- The number and percentage of subjects completing <12 months, 12, and ≥24 months of the study, where 1 month is defined as 28 days
- The overall number and percentage of subjects discontinuing and the number and percentage of subjects discontinuing by primary reason for discontinuation. If the subject discontinued the study and the Study Termination eCRF module is not available, the reason for discontinuation will be reported as “UNKNOWN”.

A summary of discontinuations due to AEs for all screened subjects will present the number and percentage of subjects who discontinued this study due to AEs broken down by type of AE.

The number and percentage of subjects enrolled under each protocol amendment (estimated by date of informed consent) will be presented. This will also be presented in the subject data listings.

The number and percentages of subjects impacted by COVID-19 will be presented for each visit, overall and by impact category, for each relationship to COVID-19 as well as any relationship, overall and by country, for all subjects in the SS. This will also be presented in the subject data listings.

## 5.2 Protocol deviations

Important protocol deviations defined in the important protocol deviations document, and additionally identified at the DEMs, will be listed. In addition, the number and percentage of subjects with at least 1 important protocol deviation will be summarized overall and by category of important protocol deviation (as defined in [Section 3.4](#)) for the SS. The number and percentage of subjects with no important protocol deviations will also be summarized for the SS.

## 6 DEMOGRAPHICS AND OTHER BASELINE CHARACTERISTICS

### 6.1 Demographics and other Baseline characteristics

Demographic variables, unless otherwise specified, will be obtained from the demographics data collected at the time of entry into the previous pediatric study.

Demographic variables will be presented by weight band (using the levels defined in [Section 3.2.10](#)), by enrollment group (using the levels defined in [Section 3.2.12](#)) and overall for the SS. The variables to be considered are:

- Age at entry into previous pediatric study (years) (as defined in [Section 3.2.9](#))
- Age at entry into EP0034 (years) (as defined in [Section 3.2.9](#)) – continuous and categorized as (28 days - <24 months, 24 months - <12 years, 12 years - <18 years)
- Gender
- Weight (kg)
- Weight (kg) at entry into EP0034
- Weight band at entry into EP0034 (as defined in [Section 3.2.10](#))
- Height (cm)
- BMI ( $\text{kg}/\text{m}^2$ ) (as defined in [Section 3.2.11](#))
- Head circumference (cm)
- Racial group (American Indian/Alaskan Native, Asian, Black, Native Hawaiian or Other Pacific Islander, White, and Other/Mixed)
- Ethnicity (Hispanic or Latino, and not Hispanic or Latino)
- Vagus nerve stimulation (VNS) use (Active VNS, No VNS, and VNS not active)

A listing of reproductive potential and birth control measures will be provided. No summaries of these results are planned.

## **6.2 Medical history and concomitant diseases**

### **6.2.1 Medical History**

The number and percentage of subjects with a medical history condition (except epilepsy), including both resolved and ongoing conditions, will be summarized overall and by MedDRA® primary system organ class (SOC) and preferred term (PT) for the SS.

### **6.2.2 Concomitant diseases and conditions**

The number and percentage of subjects with concomitant diseases and conditions (medical history conditions noted as ongoing at study entry for the EP0034 study), except epilepsy, will be summarized by SOC and PT for the SS.

## **6.3 History of epilepsy**

The history of epilepsy uses eCRF information collected at the time of entry into the previous pediatric LCM study.

### **6.3.1 History of seizure types**

The number and percentage of subjects experiencing partial-onset seizures (type I), simple partial (type IA), complex partial (type IB), and partial, secondary generalized seizures (type IC), in addition to each seizure category within such, at any time prior to study entry will be summarized based on the 1981 International League Against Epilepsy (ILAE) Seizure Classification History CRF/eCRF module. This will be summarized for the SS, by seizure classification subgroups.

For POS subjects the following classifications will be used. A subject will be classified as having a history of partial-onset seizures (I) if the subject has a history of simple partial (IA), complex partial (IB), or partial, secondary generalized (IC) seizures. A subject will be classified as having a history of simple partial seizures if the subject has a history of motor signs (IA1), somatosensory or special sensory symptoms (IA2), autonomic symptoms or signs (IA3), or psychic symptoms (IA4). A subject will be classified as having a history of complex partial seizures if the subject has a history of simple partial onset followed by impairment of consciousness with simple partial features (IB1a) or automatism (IB1b), or if the subject has a history of impairment of consciousness at onset with no other features (IB2a) or automatism (IB2b). A subject will be classified as having a history of partial, secondary generalized seizures if the subject has a history of simple partial evolving to generalized (IC1), complex partial evolving to generalized (IC2), or simple partial evolving to complex partial evolving to generalized (IC3) seizures.

For subjects with generalized seizures the following classifications will be used. A subject will be classified as having a history of partial-onset seizures (I) if the subject has a history of simple partial (IA), complex partial (IB), or partial, secondary generalized (IC) seizures. A subject will be classified as having a history of simple partial seizures if the subject has a history of motor signs (IA1), somatosensory or special sensory symptoms (IA2), autonomic symptoms or signs (IA3), or psychic symptoms (IA4). A subject will be classified as having a history of generalized seizures (II) if the subject has a history of absence (IIA), myoclonic

(IIB), clonic (IIC), tonic (IID), tonic-clonic (IIE), or atonic (IIF) seizures. A subject may also be classified as having a history of unclassified epileptic seizures (III).

### 6.3.2 History of seizure characteristics

Quantitative summaries of epilepsy duration and age at diagnosis (as defined in [Section 3.2.9](#)) will be summarized for the SS.

### 6.3.3 Historical seizure counts

The Historical Seizure Counts eCRF module records the number of seizures per pre-selected ILAE seizure code experienced by the subject during the 4 weeks prior to Baseline. These data will be provided in a subject data listing.

## 6.4 Prior and concomitant medications

A listing of all medications taken during the study will be presented. Medications ongoing from the parent study will be migrated.

### 6.4.1 Concomitant AEDs taken at the start of the EP0034 Treatment Period

Concomitant AEDs taken at the start of the EP0034 Treatment Period are defined as AEDs taken concomitantly with LCM at the time of first dose of LCM in EP0034.

The number of concomitant AEDs taken at the start of the EP0034 Treatment Period will be summarized for the SS based on the following categorization: 0 AEDs, 1 AED, 2 AEDs, 3 AEDs, and 4 AEDs. The number and percentage of subjects taking concomitant AEDs at the start of the EP0034 Treatment Period will be summarized, separately, by WHODD chemical subgroup (level 4) and medication name, for the SS.

### 6.4.2 Concomitant AEDs taken during the EP0034 Treatment Period

Concomitant AEDs taken during the EP0034 Treatment Period are defined as AEDs taken concomitantly for at least one day in common with LCM in EP0034.

The number and percentage of subjects taking concomitant AEDs during the EP0034 Treatment Period will be summarized overall and, separately, by WHODD chemical subgroup (level 4) and medication name, for the SS.

VNS is allowed and will not be counted as a concomitant AED.

### 6.4.3 Concomitant medications (excluding AEDs)

The number and percentage of subjects taking concomitant non-AEDs during the EP0034 Treatment Period will be summarized overall and, separately, by WHODD anatomical main group (level 1) and therapeutic subgroup (level 2), for the SS.

## 7 MEASUREMENTS OF TREATMENT COMPLIANCE

Information reported on the eCRF regarding LCM dispensed and returned will be reported in subject data listings. No summaries of these results are planned. LCM dosing compliance will be evaluated through the review of important protocol deviations classified under LCM Dosing Regimen (see [Section 3.4](#)).

## 8 SAFETY ANALYSES

All safety variables will be analyzed by descriptive methods on the SS.

## 8.1 Extent of exposure

All the summaries described below will also be presented for the FAS.

The duration of LCM exposure (days), as defined in [Section 3.2.7](#), will be summarized as a continuous parameter (in days) overall, and repeated by weight band using the levels defined in [Section 3.2.10](#). In addition, the duration of LCM exposure will be summarized using the cumulative 6-month time intervals for the Treatment Period, as defined in [Section 3.2.7](#).

Subject-years of LCM exposure will be summarized using the cumulative 6-month time intervals for the Treatment Period, as defined in [Section 3.2.7](#).

The maximum daily LCM dose (mg/kg/day), as defined in [Section 3.2.8](#), will be summarized overall, and repeated by weight band using the levels defined in [Section 3.2.10](#).

The modal daily LCM dose (mg/kg/day), as defined in [Section 3.2.8](#), will be summarized, overall, and repeated by weight band using the levels defined in [Section 3.2.10](#). In addition, the number of subjects and subject-years exposed in each of the modal daily LCM dose categories (mg/kg/day) will be summarized for the Treatment Period, as defined in [Section 3.2.8](#).

## 8.2 Adverse events

AEs will be tabulated by MedDRA SOC and MedDRA PT; select tables will also be presented by weight band and enrollment group using the levels defined in [Sections 3.2.10](#) and [3.2.12](#) respectively. In addition, select AE tables will also be presented by 3-month time intervals (as defined in [Section 3.2.5](#)). The number and percentage of subjects experiencing each event at least once will be summarized. All summaries will be sorted alphabetically by SOC and by frequency of events within PTs, starting with the most frequent event overall.

AEs will be classified as pre-treatment, treatment-emergent, or post-treatment. Pre-treatment AEs are defined as AEs which had an onset date prior to the first EP0034 dose of LCM. Treatment-emergent AEs (TEAEs) are defined as those events which started on or after the date of first EP0034 dose of LCM, or whose intensity worsened on or after the date of first EP0034 dose of LCM. AEs occurring within 30 days after last dose of LCM will be considered treatment emergent. Post-treatment AEs are defined as AEs which had an onset date after 30 days after the last dose of LCM.

For results disclosure on public registries (eg, ClinicalTrials.gov), treatment-emergent adverse events and treatment-emergent serious adverse events will be published.

All AEs reported during the study including pre-treatment and post-treatment AEs will be provided in a subject data listing.

An overview of the incidence of TEAEs will provide the overall summary of TEAEs and the numbers and percentages of subjects with at least 1 TEAE, with a serious TEAE, with a drug-related TEAE, with a severe TEAE, and with a drug-related serious TEAE. The number and percentage of subject discontinuations due to TEAEs, the number and percentage of all deaths (if applicable), and the number and percentage of subjects with AEs leading to death (if applicable) will also be summarized. This overall summary will be repeated by weight band and enrollment group using the levels defined in [Sections 3.2.10](#) and [3.2.12](#), respectively.

The following summaries of AEs will be provided by MedDRA primary SOC and PT:

- Incidence of TEAEs
- Incidence of serious AEs

- 
- Incidence of serious TEAEs
  - Incidence of non-serious TEAEs
  - Incidence of TEAEs leading to discontinuation from the study
  - Incidence of TEAEs by relationship to LCM
  
  - Incidence of TEAEs by maximum intensity
  - Incidence of TEAEs related to Potentially Drug Induced Liver Injury (PDILI) (defined in Appendix Section 12.3)
  - Incidence of pediatric growth-, neurodevelopment-, behavior-, and endocrine-related TEAEs (defined by manual medical review)
  - Incidence of non-serious TEAEs by relationship to LCM
  - Incidence of fatal TEAEs by relationship to LCM
  - Incidence of non-serious TEAEs occurring in at least 5% of subjects
  - Incidence of non-serious TEAEs occurring in at least 5% of subjects by relationship to LCM
  - Incidence of drug-related TEAEs by seriousness
  - Incidence of other significant TEAEs (defined in Appendix 12.2)

The following summaries of AEs will also be repeated by weight band and enrollment group using the levels defined in Sections 3.2.10 and 3.2.12 respectively.

- Incidence of TEAEs
- Incidence of serious AEs
- Incidence of serious TEAEs
- Incidence of TEAEs leading to discontinuation from the study
- Incidence of non-serious TEAEs occurring in at least 5% of subjects
- Incidence of drug-related TEAEs by seriousness
- Incidence of other significant TEAEs (defined in Appendix 12.2)

The following summaries of AEs will be presented for the 3-month time intervals (as defined in Section 3.2.5) of:  $\leq 3$  months,  $>3$  to  $\leq 6$  months,  $>6$  to  $\leq 9$  months,  $>9$  to  $\leq 12$  months,  $>12$  to  $\leq 15$  months,  $>15$  to  $\leq 18$  months,  $>18$  to  $\leq 21$  months,  $>21$  to  $\leq 24$  months, and  $\geq 24$  months:

- Incidence of all TEAEs with onset during the Treatment Period
- Incidence of all serious AEs with onset during the Treatment Period

- Incidence of all serious TEAEs with onset during the Treatment Period
- Incidence of all TEAEs leading to discontinuation from the study with onset during the Treatment Period
- Incidence of other significant TEAEs with onset during the Treatment Period (defined in Appendix 12.2)

In addition, summaries for the incidence of TEAEs overall, incidence of serious AEs, incidence of serious TEAEs, incidence of TEAEs leading to discontinuation, incidence of other significant TEAEs, TEAEs related to PDILI, and pediatric growth-, neurodevelopment-, behavior-, and endocrine-related TEAEs will be repeated presenting the site and subject number of all those subjects experiencing each TEAE as well as in subject data listings.

### 8.3 Clinical laboratory evaluations

Hematology, blood chemistry (including liver function tests), urinalysis, and endocrinology parameters are assessed throughout the study, according to the tabular schedules of study procedures. Urinalysis will be performed for subjects  $\geq 5$  years of age only.

All summaries of laboratory parameters will only summarize parameters planned based on the protocol. However, both planned and unplanned laboratory parameters will be provided in subject data listings. Summaries will include hematology, chemistry and endocrinology results; urinalysis results will be included in subject data listings only.

Observed values of hematology, chemistry, and non-gender specific endocrinology parameters (ie, thyroid stimulating hormone, triiodothyronine [total and serum-free], and thyroxine [total and serum-free]) will be summarized for each visit and Last Visit. Change from Baseline for hematology, chemistry, and non-gender specific endocrinology parameters will be summarized for all post-Baseline visits, and Last Visit. Gender specific endocrinology parameters (ie, follicle stimulating hormone, luteinizing hormone, and testosterone) will be presented similarly, by gender.

A shift table that cross-tabulates Baseline versus maximum result during the Treatment Period in categories of  $<1 \times$  ULN (upper limit of normal),  $1$  to  $<2 \times$  ULN,  $2$  to  $<3 \times$  ULN,  $\geq 3 \times$  ULN, and missing will be presented for liver function tests (LFT) which include ALT, AST, GGT, Total Bilirubin, and ALP.

Treatment-emergent markedly abnormal (TEMA) values are defined as those TEMA values during the defined Treatment Period at scheduled or unscheduled visits which occur on or after the first EP0034 LCM administration through to the end of the study but were normal at Baseline. The age at the time of assessment will be used for determining TEMA (as defined in Section 3.2.24).

The number and percentage of subjects with a TEMA value, TEMA low value, and TEMA high value will be summarized, at each post-Baseline visit and Last Visit. Percentages will be relative to the number of subjects with a value at each time point. Criteria for determining if a value is TEMA are detailed in Appendix 12.1.

Serum and urine pregnancy testing will be performed on all females of childbearing potential, according to the tabular schedules of study procedures.

Serum and urine pregnancy test results will be listed. No summaries of these results are planned.

Potential drug induced liver injury (PDILI) criteria as outlined in the protocol, will be checked at all laboratory assessments. The number and percentage of subjects meeting PDILI criteria (ie, ALT criteria and/or AST criteria and/or total bilirubin criteria, and/or presence of symptoms), will be presented by treatment group. Percentages will be based on the number of subjects with a non-missing measurement for the variable of interest at the relevant visit.

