12.3 Planned safety analyses

The long-term safety of LCM at individualized doses will be evaluated by means of the safety analyses. Summary tables will be presented over the Treatment Period by 3-month periods and by categories of total duration of exposure. All safety variables will be analyzed by descriptive methods on the SS. Treatment-emergent AEs will be defined as those events which started on or after the date of first EP0034 dose of LCM, or whose severity worsened on or after the date of first EP0034 dose of LCM. Adverse events which occur within 30 days after last dose of LCM will be considered treatment emergent. Treatment-emergent AEs will be summarized by categories of total duration of exposure, 3-month period, Medical Dictionary for Regulatory Activities (MedDRA[®]) Primary System Organ Class and Preferred Term in incidence tables. Separate tables will be provided by categories of total duration of exposure for AEs leading to withdrawal from the study and SAEs.

The safety variables such as changes in ECG, vital signs, laboratory parameters, height, body weight measurements, and Tanner Stage scores will be analyzed descriptively. The results for occurrence of these variables during long-term treatment will be summarized overall, and by visit. Subjects will be grouped by dose for summary purposes. The procedure for grouping

subjects by dose will be defined in the SAP. In addition, shift tables may be used to evaluate the number and percentage of subjects having a different post-Baseline status when compared to their Baseline status.

Changes from Baseline in laboratory, ECG, and vital sign values will be tabulated. In addition, physical and neurological examination abnormalities will be listed by visit. Markedly abnormal values will be summarized descriptively for laboratory, vital sign, body weight, and ECG parameters.

Achenbach CBCL scores, BRIEF/BRIEF-P scores, and Bayley-III scores and the respective change from primary LCM study Baseline scores will be analyzed in a descriptive manner.

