### 3.2.4 Study visit labeling

Visits will be labeled in table summaries (according to the schedule outlined in Section 5.2 of the protocol) as follows:

- "Visit X, Week X" for scheduled visits during the Treatment Period

- “Taper Visit”
- “Safety Follow-up Visit”
- “Last Visit” (see below in [Section 3.2.6](#) for further information)

Listings will also include “Unscheduled Visit” as applicable.

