### 3.2.6 Last Visit

The Last Visit for all assessments in EP0034 is the last non-missing assessment during the Treatment Period. All scheduled and unscheduled assessments within this time period will be considered. Last Visit will be determined separately for each study procedure where Last Visit is mentioned within this document.

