## 8.4 Vital signs, physical findings, and other observations related to safety

### 8.4.1 Vital signs, body weight, height, BMI, and head circumference

Vital signs (systolic BP [SBP], diastolic BP [DBP], and pulse rate) will be assessed after at least 3 minutes at rest in a supine position throughout the study, according to the tabular schedules of procedures. Body weight, height, and head circumference will also be assessed throughout the study, according to the tabular schedules of procedures.

Assessment of orthostatic changes (only in ambulatory subjects) will also be performed as follows: after the 3 minute measurement in supine position, the subject is asked to stand up, and SBP, DBP and pulse rate are taken approximately 1 minute and approximately 3 minutes after the subject stands up, as feasible.

Observed values of SBP, DBP, pulse rate, body weight, height, BMI, and head circumference will be summarized for each visit and Last Visit. Change from Baseline for SBP, DBP, pulse rate, body weight, height, BMI, and head circumference will be summarized for all post-Baseline visits, and Last Visit.

Orthostatic changes of SBP, DBP, and pulse rate will be summarized for each visit and Last Visit.

Markedly abnormal (MA) values are defined as those MA values during the defined Treatment Period at scheduled or unscheduled visits which occur on or after the first EP0034 LCM administration through to the end of the study. The age at the time of assessment will be used for determining MA (as defined in Section 3.2.24).

The number and percentage of subjects with a MA value, MA low value, and MA high value, at each post-Baseline visit and Last Visit, for which SBP, DBP, pulse rate, and body weight are scheduled to be assessed, and Last Visit, will be presented. Percentages will be relative to the number of subjects with a value at each time point.

The abnormal vital sign criteria are defined as follows:

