#### 8.4.2 Electrocardiograms (ECGs)

Standard 12-lead ECGs (2 interpretable recordings [20 to 30 minutes apart]) will be performed throughout the study, according to the tabular schedules of procedures.

For ECGs, Baseline will be defined as the average of all pre-dose interpretable readings. For all post-Baseline visits, the average of all interpretable readings at the specified visit will be used for summaries.

Observed values of ECG results will be summarized for each visit and Last Visit. Change from Baseline in ECG results will be summarized for all post-Baseline visits, and Last Visit. This will be summarized overall and repeated by weight band using the levels defined in [Section 3.2.10](#).

The number and percentage of subjects with no abnormality, an abnormal but not clinically significant finding, and a clinically significant finding, will be summarized for all visits, and Last Visit. Percentages will be relative to the number of subjects with an ECG assessment at each visit. Subjects are counted at most once at each visit based on the worst observed outcome across all abnormalities reported at that visit.

Summaries of shifts from Baseline to post-Baseline visits, and from Baseline to Last Visit will also be provided based on the categories normal, abnormal, not clinically significant, and abnormal, clinically significant.

A listing of ECG data will be provided for all subjects with other significant TEAEs in the Cardiac and ECG Related Terms category defined in [Appendix 12.2](#). A subject data listing of all ECG parameter values for all subjects will also be presented. Listings will include results from each recording and the average of all recordings.

The number and percentage of subjects with treatment-emergent ECG abnormalities will be presented for each post-Baseline visit and Last Visit. Abnormalities reported at an unscheduled visit will be summarized under the scheduled visit preceding the unscheduled visit (if the abnormality was not present already at the preceding scheduled visit). Treatment-emergent is defined as meeting the criteria at any post-Baseline visit during the Treatment Period (including unscheduled visits) and not meeting the same criteria during Baseline. The age at the time of visit/assessment will be used for determining abnormality criteria (as defined in [Section 3.2.24](#)). All ECG parameter values will be listed for subjects meeting any abnormality criteria.

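### Markedly abnormal labs and vital signs are defined to include unscheduled visits but tabulated only by visit and Last Visit, so most parameters have no count of subjects ever abnormal

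*SAP*

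**What the plan says.** **Definition.** In SAP 8.3 a treatment-emergent markedly abnormal (TEMA) laboratory value may arise in the "Treatment Period at scheduled or unscheduled visits which occur on or after the first EP0034 LCM administration". SAP 8.4.1 defines markedly abnormal (MA) vital signs and weight over the same visits.

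**Counting.** Laboratory TEMA counts "will be summarized, at each post-Baseline visit and Last Visit". For vital signs the plan is to present "The number and percentage of subjects with a MA value, MA low value, and MA high value, at each post-Baseline visit and Last Visit", restricted to visits "for which SBP, DBP, pulse rate, and body weight are scheduled to be assessed". In both sections the percentage denominator is the number of subjects with a value at that time point.

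**Labels.** SAP 3.2.4 gives four table labels: numbered Treatment Period visits, Taper Visit, Safety Follow-up Visit and Last Visit. It then adds: "Listings will also include “Unscheduled Visit” as applicable".

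**Last Visit.** SAP 3.2.6 takes the last non-missing Treatment Period assessment, and "All scheduled and unscheduled assessments within this time period will be considered".

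**ECG.** SAP 8.4.2 has an explicit rule: "Abnormalities reported at an unscheduled visit will be summarized under the scheduled visit preceding the unscheduled visit", provided the abnormality was not already present there.

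**Protocol.** For ECG, vital signs, laboratory parameters, height, weight and Tanner Stage, Protocol 12.3 says: "The results for occurrence of these variables during long-term treatment will be summarized overall, and by visit".

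**The concern.** The definition admits unscheduled values, but the tables give them no row. The plan solves this for ECGs and is silent for laboratory values and vital signs, so a programmer has to guess. Nor is any row planned that counts each subject once over the Treatment Period.

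Long-term safety is the study's primary objective, and a natural question is what proportion of children were ever markedly abnormal on a given measure. For most parameters the planned tables cannot answer it. The gap matters most for blood pressure, pulse and weight, because Protocol 8.5 has these taken at every Unscheduled Visit. Chemistry and hematology are not on that visit's list and are done there only at the investigator's discretion, although Protocol 10.6.1 requires abnormal hepatic results to be repeated, which can produce off-schedule samples.

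**Working it through.** The study is descriptive, so there is no planned figure to reproduce. The check is a reading of the text, followed by an illustration of what by-visit percentages leave open.

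**Step 1: follow an unscheduled abnormal value through the plan.**

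- *Blood pressure, pulse, weight:* qualifies as MA; has no row, because rows are limited to visits where the measure is scheduled; appears in a table only if it is the Last Visit value; otherwise in listings.
- *Hematology and most chemistry:* qualifies as TEMA if normal at Baseline. SAP 8.3 refers to each post-Baseline visit and does not say scheduled, so exclusion here rests on the labels in SAP 3.2.4. On that reading the result is the same.
- *ALT and AST:* SAP 8.3 cross-tabulates Baseline against the maximum Treatment Period result, with a top category of at least 3×ULN. That equals the lower marked-abnormality cut in SAP Table 12–2, so subjects ever at or above 3×ULN are shown. The 5×ULN cut is not separated.
- *GGT and ALP:* in the same shift table, but its top category matches the marked-abnormality criterion only from age 17; below that the criteria are fixed values.
- *Total bilirubin:* in the shift table, but the criterion is a fixed 2.0 mg/dL.
- *Potential drug-induced liver injury (PDILI):* SAP 8.3 checks the criteria at all laboratory assessments and counts subjects meeting them.
- *ECG:* mapped to the preceding scheduled visit, but with no any-time row.

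**Step 2: what by-visit percentages imply.** Let p be the share abnormal at each of k visits and N the number of subjects.

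- Smallest number ever abnormal (same children each time): N × p
- Largest (different children each time): the smaller of N and k × N × p
- Independent visits: N × [1 − (1 − p)^k]

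Inputs: N = 500 is the approximate number eligible (Protocol 12.8, SAP 2.4). From Protocol Tables 5-1 and 5-2, k = 4 for chemistry and hematology after Visit 1 (Weeks 20, 52, 72, 96) and k = 12 for vital signs and weight (Visits 2 to 13). The documents give no value for p, so it is assumed and varied.

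| Measure | p (assumed) | Smallest | Independent | Largest |
|---|---|---|---|---|
| Laboratory, k = 4 | 0.5% | 2.5 | 9.9 | 10 |
| Laboratory, k = 4 | 1% | 5 | 19.7 | 20 |
| Laboratory, k = 4 | 2% | 10 | 38.8 | 40 |
| Vital sign, k = 12 | 0.5% | 2.5 | 29.2 | 30 |
| Vital sign, k = 12 | 1% | 5 | 56.8 | 60 |
| Vital sign, k = 12 | 2% | 10 | 107.6 | 120 |

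Example: with k = 12 and p = 1%, the smallest is 500 × 0.01 = 5, the largest 12 × 5 = 60, and independence gives 500 × (1 − 0.99^12) = 56.8. Children abnormal only at an Unscheduled Visit would be additional.

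**The case against.** Several points on the other side stand, and they limit the claim.

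- **Nothing is lost from the record.** A reader might infer that unscheduled values disappear or that the ever-abnormal count is unobtainable. The documents do not support that. All data are listed, MA vital signs have their own listing, and Last Visit can take an unscheduled value. The count could be made by hand; it is not tabulated.
- **Some worst-value tables exist.** It would be wrong to say that no table shows how many children were ever markedly abnormal: the liver shift table and the PDILI count are real exceptions.
- **The primary safety variables are not affected.** They are incidences of treatment-emergent adverse events (TEAEs); laboratory values and vital signs are other safety variables. Abnormalities reported as adverse events are counted once per subject whatever visit found them, and bradycardia is among the other significant TEAEs. This covers only abnormalities that were reported as events.
- **An undeclared departure from the protocol is not established.** A reader might take Protocol 12.3 to promise an any-time count that SAP 3.9 fails to list as dropped. But the word for overall there may mean all subjects combined, as it often does in the SAP, and the protocol's separate sentence on markedly abnormal values asks only for a descriptive summary.
- **The illustration is soft.** The upper bound needs no child to be abnormal twice. That is implausible for weight below age 17, where the criterion is a growth-curve percentile and tends to persist. Taper and Safety Follow-Up Visits are left out of k.

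**Conclusion.** The gap is real but narrower than the section wording first suggests. For blood pressure, pulse, weight, hematology and most chemistry, a qualifying value found at an Unscheduled Visit is listed but not tabulated unless it is the last Treatment Period value, and no table states how many subjects were ever markedly abnormal. The exceptions are ALT and AST at or above 3×ULN and the PDILI count. ECG lacks only the any-time count.

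At an assumed 1% to 2% per visit and 500 subjects at every visit, the by-visit tables are compatible with 5–20 to 10–40 children for a laboratory parameter and 5–60 to 10–120 for a vital sign. These ranges show that the planned tables leave the figure open; they do not predict it. They rest on unsourced rates, on all eligible subjects enrolling and on no dropout. For laboratory values the conclusion also depends on reading the table labels in SAP 3.2.4 as complete.

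**What to change.** In SAP 8.3 and 8.4.1, and in 8.4.2 for consistency, add one row to each marked-abnormality table: *any time during the Treatment Period (scheduled and unscheduled)*. Count each subject once per parameter and direction, with subjects having at least one value after the first EP0034 dose as the denominator.

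Also state how unscheduled laboratory and vital-sign values enter the tables: either through that row alone, or by mapping to the preceding scheduled visit as for ECGs. Mapping alone would not be enough, since it still gives no any-time count.

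The cost is a few lines of SAP text and one extra row per table. No new data are needed.
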